**tDCS for Increasing Exercise Adherence in Individuals with Elevated Depressive
Symptoms**

NCT03178903

February 21, 2018

Background

Depressive symptoms predict poor exercise adherence. (1, 2) (3)-(4) (5-7) (8) (9) (10) (11) (12) and depression-specific characteristics (e.g., affect) are related to physical activity (PA) levels. A cardinal symptom of depression is dysregulated affect – i.e., lower levels of positive affect and higher levels of negative affect (13, 14). Positive affect has been consistently identified as a significant correlate of PA levels across a myriad of populations including: Parkinson's (15), arthritis (16), ovarian cancer survivors (17), dementia (18), cardiovascular disease (1, 19), osteoporosis (20), knee patients (21), and college students (22, 23). On the other hand, negative affect is inversely related to PA (1, 17, 21, 22, 24). The dysregulation in affect seen in depression is particularly concerning when it comes to PA level. Those with elevated depressive symptoms are placed at a disadvantage for maintaining regular physical activity in the long-term.

Affective responses to exercise can influence exercise adherence. While individuals almost universally “feel good” after engaging in PA(25), there is a fair amount of affective variability *DURING* exercise – some individuals increase in positive affect and others in negative affect (26-28). In particular, increases in positive affect predict both intentions to engage in exercise(29) and actual exercise behavior (28, 30-33). While research on the affective experiences of exercise in those with depression has been limited, recent work suggests that those with a history of depression experience less of an increase in positive affect following PA(34). Higher levels of depressive symptoms has also been associated with greater perceived physical exertion with exercise (35) and, in our own work, reduced PA enjoyment. Therefore, if those with depression experience exercise as more challenging and less rewarding than nondepressed individuals, it can impact their likelihood of maintaining PA in the long-term.

While physiological cues overwhelm the affective experience at higher exercise intensities, cognitive factors (e.g., self-regulation, attentional bias) influence affect at lower intensities (dual mode theory; (36)). For example, negative mood also appears to be interfere with obese, sedentary individuals' ability to self-regulate physical activity resulting in lower levels of exercise participation (37). Further the inability to direct attention away from unpleasant stimuli (i.e., attentional bias; (38, 39)) is a hallmark of depression (40) resulting in negative affect. Individuals with affective disturbances experience difficulty with attentional bias toward unpleasant emotions during exercise(41).

Additionally, a growing body of electroencephalogram (EEG) studies support the notion that exercise is an emotion-eliciting event (42). A recent review of 11 EEG studies examining the relation between affect and PA (43) concluded that a single session of exercise results in an asymmetric pattern of activity in the prefrontal cortex: greater left frontal activity before exercise is associated with greater positive affect during exercise, whereas, greater right frontal activity results in increases in negative affect during exercise. This is particularly relevant for individuals with depression who, in both EEG and fMRI studies, have been found to show greater relative activity in right vs. left DLPFC (44) (45). Given the inherent difficulties in regulating affect experienced by depressed individuals, they may be “handicapped” in their ability to positively experience exercise, which may contribute toward their lower levels of physical activity. Yet, regular physical activity is critical for decreasing health risks (e.g., obesity, diabetes, heart disease) in this population and interventions to improve the affective experience of PA could have a high public health impact.

Transcranial direct current stimulation (tDCS) as a novel approach toward regulating affective processes. tDCS is a form of noninvasive brain stimulation which has been investigated in a broad range of populations (46, 47), and has shown promise in impacting a wide variety of cognitive and affective processes, such as working memory (e.g., (48, 49)), motor learning (e.g. (50, 51)) and emotion regulation (e.g., (52-54)). tDCS uses low current electricity (typically 1-2mA) to modulate neuronal excitability in targeted brain areas via two electrodes placed on the head. tDCS acts via slight alterations to membrane potentials in areas underlying electrodes, with typical settings (e.g., two electrodes, 1mA current) resulting in increased likelihood of neuronal firing under the anode and decreased likelihood of neuronal firing under the cathode. As tDCS modulates the likelihood of neuronal firing, but does not directly induce an action potential (like transcranial magnetic stimulation; TMS), it may be particularly promising in combination with behavioral interventions to enhance activity in neural circuits already in use. tDCS has been used in a large number of individuals and has been found to be relatively safe, with the vast majority of reported side effects being mild and transient (e.g., headache, fatigue; (55)). Moreover, tDCS has practical benefits over other forms of neuromodulation (e.g., TMS, deep brain stimulation) as it is significantly less costly and more

portable, making it more practical for widespread implementation (see Image).

While tDCS of DLPFC has been investigated as an intervention for depression with some (though not universal) support for efficacy (46, 56-58), studies have suggested tDCS of DLPFC may improve cognitive control over emotional information (52-54, 59, 60) and corresponding reductions in the emotional valence of negative stimuli. Interestingly, these changes do not appear to be explained by a change in mood, further supporting the notion that differences observed are likely due to improved cognitive control over emotional material (53, 60). Consistent with these findings, in depressed patients reduced attentional bias to emotional stimuli has been found following anodal tDCS to DLPFC(54). Given the central role of the affective experience of exercise to long-term PA and given experimental findings relating tDCS of DLPFC to improved emotion regulation, the combination of tDCS (of DLPFC) with an exercise program may be a promising approach to improve exercise adherence.

Experimental Method

Brief Description of Subjects

Eligible participants will: (a) be between 18 and 65 years of age, (b) be low active (i.e., less than 90 min of moderate-intensity exercise/wk for the past 6 mos.), (c) have elevated levels of depressive symptoms (i.e., Center for Epidemiological Studies Depression Scale score ≥ 10), (d) be interested in starting an exercise program in the next month, and (e) able to walk one mile on a treadmill. Exclusion criteria include: (a) history of mania or hypomania, (b), history of psychotic disorder, (c) current DSM-5 diagnosis of anorexia nervosa, bulimia nervosa, or other eating disorder for which an exercise intervention would be contraindicated, (d) DSM-5 moderate and severe substance use disorder (e) current suicidality or homicidality, (f) current DSM-5 diagnosis of major depressive disorder (MDD) that is not currently being treated with pharmacotherapy or psychotherapy (g) physical disabilities or medical problems that would prevent participation in moderate intensity exercise (i.e., physician denied medical clearance), may be contraindicated for tDCS (e.g., seizure disorder), or other study procedures (e.g., contagious skin disease), (h) current pregnancy or intent to become pregnant during the next 8 weeks, (i) pacemaker or metal implanted in the cranial cavity, (j) psychiatric medication changes within 6 weeks prior to study entry.

Study Design

The goal of the proposed study is to test the preliminary efficacy of tDCS combined with an 8-week aerobic exercise intervention for increasing adherence to exercise in individuals with elevated depressive symptoms. Participants will be randomized to receive the 8-week exercise intervention plus anodal tDCS of DLPFC (AE+tDCS) or sham tDCS of DLPFC (AE+sham). Outcomes will be assessed at end-of-treatment (EOT) as well as at 3-and 6-month follow-up.

Specific Procedures or Treatments

Initial Screening and Medical Clearance Procedures. Interested individuals will contact our research staff and we will conduct a screening of participants' current level of physical activity and depressive symptoms. Participants appearing to meet study criteria will be scheduled for a more comprehensive baseline assessment. Research staff will obtain informed consent and then participants will be evaluated using the diagnostic and screening measures detailed below to confirm eligibility.

Participants will also complete a brief computer task at the initial appointment and at the end of the 12-week program that is designed to test working memory. The task involves matching letters to those on screen and lasts approximately 10 minutes. At this interview, we will obtain a release of information to contact their primary care physician (PCP) to request medical clearance for engaging in moderate-intensity exercise AND for engaging in tDCS. In addition to the PCP's own clinical judgment, the PCP will be provided with a list of medical issues that would exclude the participant from exercise and/tDCS. We have successfully used this approach in previous exercise intervention studies. Upon receiving medical clearance, participants will undergo a standardized 1-mile Rockport treadmill walk test, administered by an exercise physiologist, in order to obtain a baseline measure of cardiorespiratory fitness.

Study Assessments. All participants will complete a baseline assessment, as described above, as well as follow-up interviews at EOT and 3- and 6-months after baseline. Assessments will include

evaluator-administered interviews and self-report questionnaires, as well as measures of physical health and activity level (e.g., body composition, blood pressure, accelerometry). Additionally, the SAFTEE-SI will be administered weekly to assess for side effects of the intervention (see Human Subjects section for additional detail). Specific assessments to be used and the timepoints at which they will be administered are presented in Table 1 (below). Participants will be completing questionnaires on a laptop computer or tablet device, using REDCap (see Data Analysis Overview), for ease of data collection. From our prior experience conducting exercise interventions in psychiatric populations, we expect to be able to contact 80-90% of participants at follow-ups.

Randomization and Intervention Conditions. After the medical clearance, participants will be randomized to AE+tDCS or AE+sham. These conditions will differ only in whether active or sham tDCS is being delivered. Participants, evaluators, and those delivering the tDCS will all be blinded to condition. Each intervention session will begin with 20 minutes of either active or sham tDCS, followed by supervised aerobic exercise.

tDCS. tDCS is a form of noninvasive brain stimulation which uses low amplitude current (typically 1-2 mA) to modulate excitability of underlying cortex (61). The stimulation is delivered via two electrodes placed on the scalp. Current passes between them resulting in altered cortical excitability. If tDCS is delivered for a sufficient duration (e.g., >10 min,) these excitability changes have been found to persist for up to 1 hour (62, 63). The device is battery-powered and is adjustable in intensity and duration of stimulation delivered. A review of clinical research with tDCS noted that “tDCS has been tested in thousands of subjects worldwide with no evidence of toxic effects to date” (46). The most common side effects include mild local sensations at the electrode sites, including tingling or itching, (55, 64) moderate fatigue, and headache (64).

In the present study, each participant will undergo a 20-minute session of either active or sham tDCS of DLPFC during each intervention session in a between-subjects design. Each session of tDCS will be immediately followed by the supervised AE (see “Aerobic Exercise Component” section below). Active tDCS intensity will be 1 mA. The anode and cathode are each contained in a 5x5cm rectangular sponge (25 cm²). The anode will be placed over left DLPFC (F3 on the EEG 10-20 system) and the cathode over the contralateral supraorbital region (just above the right eyebrow). Stimulation will be delivered via two saline-soaked surface sponge electrodes and a battery-driven, constant current stimulator (NeuroConn DC Stimulator Plus). This device includes a study mode, in which subject-specific codes are entered to deliver active or sham stimulation, keeping the administrator blinded. Sham stimulation will use a “ramp up/ramp down” method in which stimulation will be ramped up and back down over a 30-second period. This approach has been found to be an effective sham condition in previous studies using tDCS at 1-2mA (49, 56, 65). Immediately following the 20-minute tDCS period participants will engage in a supervised moderate-intensity aerobic exercise session. These procedures will occur 3x/week for 8 weeks.

Aerobic Exercise Component. After having received either tDCS or sham, participants will engage in an AE session at Butler Hospital’s Fitness Facility. Exercise sessions will be 20-30 minutes of moderate-intensity aerobic exercise on a treadmill. These sessions will be supervised by an exercise physiologist who will monitor their heart rate and blood pressure to ensure safety and that activity is occurring at a moderate-intensity (i.e., 64-76% of age predicted maximal heart rate). Participants will be asked to rate their affect and RPE (see C.9.b) during exercise sessions. Sessions will include a 5-min warm-up and a 5-min cool-down to ensure safe exercise procedures. Participants will be asked to answer questions about affect before, during, and after exercise. An additional working memory task that involves remembering numbers will be completed three times during the AE intervention (detailed above). In the later weeks of the study, participants will be instructed to gradually increase physical activity outside these supervised sessions toward a goal of 150 minutes of moderate-intensity aerobic exercise per week. Participants will be provided with resources for increasing their physical activity at home.

Fitbit Alta activity tracker. Participants will be asked to wear the Fitbit Alta activity tracker daily. A g-mail account will be created for each participant in order to register the trackers on Fitbit.com. In doing so, the investigators will have access to the participant’s activity data throughout the course of the study. No identifying information will be entered into this account. The participant will not be given

access to this account, in order to allow tracking of activity while reducing effect of the Fitbit on behavior. Participants will be able to see the display on the Fitbit Alta tracker, which provides data for the day it is being worn. We will sync the participant's Fitbit at each session using a study computer.

Data Analysis

Sample Size Considerations. We aim to have a total of 60 participants complete the study (approximately 30 per group). Based on our previous work, we expect approximately 10-20% attrition. Therefore, we will aim to enroll a total of 72 participants to obtain our desired sample size of 60. **Primary Hypotheses:** We will first examine patterns of missing data to determine possible mechanisms of missingness and will explore different techniques to impute missing data values^{145,146}. To test our first primary hypothesis, we plan to use a mixed modeling approach to test for differences in MVPA between conditions across time-points (EOT, 3- and 6-month follow-up). To test our second aim 1 hypothesis, we will conduct a between-groups t-test to examine whether session attendance differs between groups during the 8-week intervention.

4. Aikens JE. Prospective associations between emotional distress and poor outcomes in type 2 diabetes. *Diabetes care*. 2012;35(12):2472-8.

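### The primary MVPA mixed model names no baseline MVPA term, so as written it gives up precision that baseline adjustment could recover at almost no cost

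*Combined protocol and SAP*

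**What the plan says.** The Primary Hypotheses paragraph under Data Analysis is the only description of the primary MVPA model: a mixed model to "test for differences in MVPA between conditions across time-points (EOT, 3- and 6-month follow-up"). No covariate, change score or baseline occasion is named there or elsewhere.

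On the data available, Study Assessments states: "All participants will complete a baseline assessment, as described above". The battery is described "as well as measures of physical health and activity level (e.g., body composition, blood pressure, accelerometry"). The schedule is deferred to a table: "Specific assessments to be used and the timepoints at which they will be administered are presented in Table 1 (below"). That table is not in the text we have, so accelerometry at baseline is an inference. Randomization follows medical clearance, which is requested at the baseline interview, so the baseline assessment itself precedes randomization.

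Two other statements bear on how well baseline MVPA would predict later MVPA. Entry requires "less than 90 min of moderate-intensity exercise/wk for the past 6 mos", and in the later weeks participants are steered "toward a goal of 150 minutes of moderate-intensity aerobic exercise per week".

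**The concern.** A baseline value of the outcome is often a useful predictor of its later values, and adjusting for it removes the part of the outcome variance that it explains. A trial of about 30 completers per arm has little precision to spare, and extra participants cost far more than an extra model term.

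Silence on the point also leaves a choice open. Adjusted and unadjusted versions of the model would both fit the plan's wording, so the choice could be made after the data are seen. Stating the term in advance closes that.

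No bias is alleged.

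**Working it through.** **Plan's own figure.** The only sample-size arithmetic is 72 enrolled for 60 completers. This implies attrition of 1 − 60/72 = 16.7%, inside the stated 10–20%. (At the full 20%, 60/0.80 = 75.) No power, alpha, SD or effect size is stated, so there is no power figure to reproduce.

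**Inputs.** From the plan: N = 60 completers, about 30 per arm. Assumed: two-sided 5% test, 80% power as the reference, outcome SD = 1, correlation r between baseline and each follow-up, and correlation f between follow-ups.

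**Single visit.** Adjustment multiplies the variance by (1 − r²). Estimating the slope costs a factor 1 + 1/(N − 4) = 1 + 1/56 = 1.0179.

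- Net reduction = 1 − (1 − r²) × 1.0179.
- Extra completers of equal worth = 60 × net/(1 − net).
- Detectable difference: unadjusted 0.7356 SD (t test, 58 df); adjusted 0.7358 × √[(1 − r²) × 1.0179] (57 df).

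| r | Gross reduction | Net reduction | Worth in completers | Detectable difference (SD) |
|---|---|---|---|---|
| 0 | 0% | −1.8% | −1 | 0.742 |
| 0.2 | 4% | 2.3% | +1 | 0.727 |
| 0.3 | 9% | 7.4% | +5 | 0.708 |
| 0.5 | 25% | 23.7% | +19 | 0.643 |

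At r = 0.1 the net effect is still a loss, of 0.8%. Break-even is r = √(1 − 1/1.0179) = 0.13. A simulation of 40,000 trials per value gave net reductions of −2.1%, −0.9%, 2.0%, 7.6% and 23.4% at r = 0, 0.1, 0.2, 0.3 and 0.5, in agreement with the formula.

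At the effect for which the unadjusted test has 80% power (0.736 SD), adjusted power is 79.3%, 80.9%, 82.9% and 89.4% at r = 0, 0.2, 0.3 and 0.5.

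**Average of the three visits** (a contrast the plan does not name). The unadjusted variance is proportional to (1 + 2f)/3, and adjustment subtracts r². The gross reduction is r² ÷ [(1 + 2f)/3]; the net figure applies the same 1.0179.

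| f | r | Gross reduction | Net reduction |
|---|---|---|---|
| 0.2 | 0.2 | 0.04/0.467 = 9% | 7% |
| 0.3 | 0.3 | 0.09/0.533 = 17% | 15% |
| 0.5 | 0.5 | 0.25/0.667 = 37.5% | 36% |
| 0.6 | 0.2 | 0.04/0.733 = 5% | 4% |
| 0.6 | 0.3 | 0.09/0.733 = 12% | 11% |

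**Condition-by-time test.** If baseline correlates equally with every follow-up, its contribution cancels in differences between visits, and the gain is about nil.

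**Chance imbalance.** The baseline difference between arms has SD √(2/30) = 0.26 SD. An imbalance of that size moves the unadjusted estimate by r × 0.26 = 0.05, 0.08 or 0.13 SD at r = 0.2, 0.3 or 0.5. This is the same r² share of variance seen from another side, not a second loss to be added.

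**The case against.** The strongest reply is that silence is not a decision. The parenthesis lists outcome occasions, and a model with baseline as a covariate would list the same three. The paragraph is an outline that also omits the covariance structure and the contrast. The text reads like an excerpt: it cites references 145 and 146 when the list ends at 65, and refers to a section C.9.b that is not there. This stands as a limit on inferring intent. It does not supply the missing term, and someone following the sentence as written would fit no baseline.

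Second, the gain may be trivial. The entry limit and the push toward the activity goal may both lower r. At r = 0.2 the gain is worth about one completer, below 0.13 there is a small loss, and a condition-by-time reading could leave nothing to gain. All of this stands. It limits the expected benefit but does not turn the change into a risk, since the loss is capped at about 2% in variance.

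Third, the instrument that yields MVPA is never named. Accelerometry is given as an example, and a Fitbit is worn daily and synced at sessions. If MVPA came from the Fitbit, the text does not establish a pre-randomization value. This also stands, and it makes confirmation of the measurement a condition of the fix.

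Finally, the study seeks only preliminary efficacy and makes no power claim that this undermines. That bears on the weight of the point: it is an improvement the plan should make, not a flaw that invalidates it.

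**Conclusion.** The concern holds as an efficiency point. The plan's only statement of the primary model contains no baseline MVPA term, and adding one is very likely feasible with data already collected. For a comparison at one visit with 60 completers, the net variance reduction runs from 2.3% at r = 0.2 to 23.7% at r = 0.5, against a worst case of 1.8% lost at r = 0. For the three-visit average it is 4% to 36% over the combinations shown.

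These figures rest on assumed correlations, complete data on 30 per arm, and a contrast that compares arms at or averaged over visits. Confidence in the size is moderate at best, because r is unknown and the assessment table is not available. That no baseline term is specified, and that the downside is small, do not depend on r.

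**What to change.** State in the Primary Hypotheses paragraph that the mixed model for MVPA at EOT, 3 and 6 months includes baseline MVPA as a covariate, with a baseline-by-time interaction. An alternative is to include baseline as a time-point with a mean constrained to be common to both arms. The two serve the same purpose when baseline is complete. They differ when it is not: the covariate version drops participants without a baseline value unless it is imputed, whereas the constrained version keeps them. The plan should therefore name one.

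In the same place, name the instrument that defines MVPA and confirm that it is measured before randomization. The primary contrast and covariance structure also need stating, but that is a separate matter.

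The cost is a sentence or two in the plan, and no new data if accelerometry is done at baseline as the assessment section suggests. The statistical cost is about 2% in variance if baseline proves uninformative. If MVPA is not measured before randomization, a baseline measurement would have to be added first, and the change would no longer be almost free.

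### The attendance comparison is a valid but unadjusted t-test; prespecifying the entry CES-D score as a covariate is a cheap, probably modest gain in precision

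*Combined protocol and SAP*

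**What the plan says.** The Data Analysis section, under Primary Hypotheses, gives the attendance analysis in one sentence: "we will conduct a between-groups t-test to examine whether session attendance differs between groups during the 8-week intervention". It names no covariate, and the randomization paragraph describes no stratification by symptom severity.

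Three other places bear on this:

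- **Premise.** The Background begins "Depressive symptoms predict poor exercise adherence". Session attendance is the adherence measure that this test uses.
- **Availability.** Inclusion criterion (c) in Brief Description of Subjects requires "Center for Epidemiological Studies Depression Scale score ≥ 10", with no stated upper limit.
- **Timing.** Under Initial Screening and Medical Clearance Procedures, on first contact "we will conduct a screening of participants' current level of physical activity and depressive symptoms". Allocation comes later: "After the medical clearance, participants will be randomized to AE+tDCS or AE+sham". The CES-D score is therefore a pre-randomization value.

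The target is 60 completers, about 30 per group, from 72 enrolled, and "we expect approximately 10-20% attrition". The documents state no alpha, power, effect size, attendance SD or CES-D/attendance correlation.

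**The concern.** Attendance has no baseline value of its own, so the only way to use baseline information in this comparison is through a predictor. The plan's rationale supplies one, and eligibility screening already records it. A two-sample t-test cannot use it. Whatever part of attendance CES-D explains stays in the error term, and a chance difference in severity between arms cannot be allowed for in the one allocation that is realized.

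With 60 to 72 participants, precision is scarce. If a visible severity imbalance appears and no covariate was prespecified, any later adjustment will be open to the charge of having been chosen after seeing the data.

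**Working it through.** **Inputs.** From the documents: 60 completers, about 30 per group; 72 enrolled, which is 36 per arm if allocation is equal; 24 scheduled sessions (3 per week × 8 weeks); CES-D taken before randomization. Assumed, because not stated: two-sided alpha 0.05, a true arm difference of d = 0.5 SD, approximate normality, and rho from 0 to 0.4.

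**Plan's own figure.** 60/72 = 0.833, so 72 enrolled corresponds to 16.7% attrition, inside the stated 10–20%. The two sizes checked are thus 30 per arm (completers only) and 36 per arm (everyone enrolled contributes a session count).

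**Unadjusted t-test.** The noncentrality is d × √(n/2).

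- n = 30: 0.5 × √15 = 1.936, df 58, critical value 2.002, power 47.8%.
- n = 36: 0.5 × √18 = 2.121, df 70, critical value 1.994, power 55.3%.

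**Adjusted for CES-D alone.** With N the total sample, the expected variance of the arm difference is multiplied by V = (1 − rho²) × (1 + 1/(N − 4)). The second factor is the expected cost of chance covariate imbalance when the slope is estimated. The noncentrality is divided by √V, and one degree of freedom is lost.

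| rho | V, 30 per arm | Power, 30 per arm | V, 36 per arm | Power, 36 per arm |
|---|---|---|---|---|
| t-test | 1 | 47.8% | 1 | 55.3% |
| 0 | 1.018 | 47.1% | 1.015 | 54.6% |
| 0.2 | 0.977 | 48.6% | 0.974 | 56.3% |
| 0.3 | 0.926 | 50.7% | 0.923 | 58.6% |
| 0.4 | 0.855 | 53.9% | 0.852 | 62.0% |

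Simulation of 20,000 trials per rho at 30 per arm, run at d = 0.736 where the t-test has 80% power, agreed with the same formula to within about half a point.

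**Break-even.** V = 1 when rho² = 1/(N − 3). That gives |rho| = √(1/57) = 0.13 at 30 per arm and √(1/69) = 0.12 at 36 per arm.

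**Equivalent sample size.** At 72 enrolled, 72/V is 73.9, 78.0 and 84.5 at rho 0.2, 0.3 and 0.4: about 2, 6 or 12 extra participants.

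**Effect of the entry cut-off.** If truncation at 10 shrinks the CES-D SD to a fraction u of its unrestricted value, then r′ = r·u/√(1 − r² + r²u²). Taking u = 0.5 to 0.8 (assumed), an unrestricted r of 0.3 becomes 0.16 to 0.24. At 30 per arm the variance reduction is then only about 1% to 4%.

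**Second covariate.** Adding treated MDD (yes/no) changes the factor to V = (1 − R²) × (1 + 2/(N − 5)). At a joint R² of 0.04, power is 47.9% (30 per arm) and 55.7% (36 per arm), almost no gain over the t-test. Break-even R² is about 3.5% and 2.9% respectively.

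**Size of a chance imbalance.** The standardized CES-D difference between arms has SD √(2/n), which is 0.26 at 30 per arm and 0.24 at 36. At rho 0.3, a one-SD imbalance moves the attendance contrast by 0.07 to 0.08 SD, and one at the 1.96-SD limit moves it by 0.14 to 0.15 SD.

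**The case against.** The strongest reply is that nothing is wrong with the t-test. Under randomization it is unbiased, and its standard error already allows for chance imbalance in CES-D. For a study of preliminary efficacy with about 30 completers per group, a plain two-sample comparison is transparent and defensible. That stands. A reader might infer that an imbalance in severity biases the attendance result or passes into it in full. It does not: it enters only in proportion to rho, and it averages out over allocations.

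The second reply is that the Background premise is general. It does not establish that severity predicts attendance at supervised sessions among people who all score 10 or more. The exclusions for untreated current MDD, current suicidality and recent psychiatric medication change may thin the upper end as well. This also stands, and it is why a reader should not infer that the extra precision is guaranteed or free. Below |rho| of about 0.13 the adjusted analysis is slightly worse.

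A third reply is that attendance is bounded at 0 to 24 and may be skewed, which a linear model does not address. True, but the planned t-test has the same limitation, so this does not separate the two.

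What survives the replies is the asymmetry: a loss of under one point of power if CES-D is irrelevant, against a gain of about 3 to 7 points if rho within this sample is 0.3 to 0.4.

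**Conclusion.** The point holds as a low-cost efficiency improvement. The planned test is valid, but it leaves out a pre-randomization covariate that the plan's own premise links to adherence and that eligibility already requires. The expected gain is modest: roughly 1 point of power at rho 0.2, 3 at 0.3 and 6 to 7 at 0.4. If the entry cut-off attenuates the correlation, the lower end is the more realistic. These figures rest on an assumed two-sided 0.05 level, d = 0.5 SD, approximate normality and correlations that the documents do not supply.

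It might seem natural to add treated MDD too, since exclusion (f) lets treated MDD and symptoms without MDD into the same sample. The documents do not support that step. They give no size or direction for an MDD effect on attendance, the variable probably overlaps with CES-D, and its cost takes up most of a small gain.

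**What to change.** Prespecify, as the primary attendance analysis, a linear model of sessions attended (0 to 24) on arm and pre-randomization CES-D entered as a continuous covariate. State which CES-D value is used (screening or baseline) if both exist. Report the adjusted arm difference with its 95% CI, and keep the unadjusted t-test as a supportive analysis. Do not add treated MDD as a second covariate.

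The change is one sentence in the Data Analysis section, made before unblinding. It needs no new data and no change to recruitment. The price is one degree of freedom and, if CES-D is unrelated to attendance, a fall in power from 47.8% to 47.1% (30 per arm) or from 55.3% to 54.6% (36 per arm).
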